Highly effective medications to treat and prevent the complications of chronic disease have been developed and evaluated. While rates of prescribing effective therapies have improved substantially, long-term adherence remains exceptionally poor. Nearly 50% of patients become non-adherent within a year of treatment initiation. Interventions that succeed in improving medication adherence may confer important clinical benefits across large populations, and may even be cost-saving by reducing rates of costly clinical outcomes such as myocardial infarction and stroke.

The success of interventions to improve adherence has been relatively limited, either because of the nature of the intervention or their broad applications to patients who do not require them or will not benefit from them. Prior studies have also been limited by recruiting small samples of volunteers, following patients for short periods, and not evaluating their impact on clinical outcomes. The efficacy of future efforts is likely to be increased by targeting interventions to patients demonstrating both poor adherence and poor disease control, tailoring interventions to individual patient needs, and touching larger and more representative patient populations and care settings. These goals can be achieved by the innovative use of information technology including electronic health records (EHR) and other advanced communication technologies, including texting.

We propose a cluster randomized controlled trial (RCT) of a novel tele-pharmacist based intervention to improve adherence to medications for hypercholesterolemia, hypertension, and diabetes. We will evaluate an innovative intervention that uses of EHR data to identify 4076 adult patients cared for by approximately 150 primary care physicians who are both non-adherent and not achieving recommended clinical targets for glycemic, blood pressure, and cholesterol control in a real-world primary care setting. Following EHR-facilitated referral from the treating primary care physicians, a clinical

pharmacist will direct an outreach program using multiple communication technologies including a telephone consultation, text messaging and video visits to improve medication adherence.

Study setting

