This trial is being conducted at Harvard Vanguard Medical Associates (Harvard Vanguard), which is a practice of Atrius Health, a large multispecialty medical group and a Pioneer Accountable Care Organization. Harvard Vanguard employs approximately 150 primary care physicians (PCPs) who provide care for approximately 300,000 adult patients at 17 practice sites. Of these, 15 practice sites have integrated retail pharmacies, where approximately 50% of patients obtain their prescription medications. Within each site, all PCPs and their eligible patients will be randomized to the same study arm.

Study design and randomization

STIC2IT is a pragmatic, prospective, intention-to-treat, cluster-randomized controlled trial designed to test the impact of a technologically-enabled, behaviorally-targeted pharmacist intervention designed to improve medication adherence and disease control among the specific group of individuals who are most likely to benefit from this intervention – those who are non-adherent to their glucose lowering, anti-hypertensive, or statin medications and have evidence of poor disease control based on recommended clinical targets. We randomly selected 1 of the 15 Harvard Vanguard practice sites with onsite pharmacies as a pilot site for intervention refinement. The remaining 14 Harvard Vanguard practice sites were then cluster-randomized such that all PCPs and their patients in a given practice site were assigned to the same study arm. Because the practice sites differ from each other, simple cluster randomization may have resulted in imbalances in patient or provider factors that could potentially bias outcome assessment. Therefore, we categorized the practice sites based on their size (i.e., small or large, based on the number of patients receiving care at each site) and whether clinical pharmacists at the sites

offered disease management counseling directly to patients (i.e., yes or no). Within the resultant 4 blocks, practices were then randomized in a 1:1 ratio to intervention or control using a random number generator.

Subjects

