To identify individuals who would benefit most from the intervention, a patient is defined as being non-adherent if they (1) have been less than 80% adherent to the specific class of medications used to treat the condition(s) for which they were being identified as being poorly controlled and (2) if their “average of averages” PDC for all eligible study drugs is less than 80%. For example, patients with poorly

controlled diabetes who are non-adherent to their diabetes medications but adherent to their statins and antihypertensives, would only be eligible if their average adherence across all 3 conditions is less than 80%. Patients are excluded if, prior to randomization, they have less than 6 months of continuous enrollment in the health plan (to allow adequate assessment of eligibility), are < 18 or > 85 years of age, or have no available telephone contact information, which would preclude contact for enrollment and delivery of the intervention.

Study procedures

Once identified, PCPs of potentially eligible intervention group patients will be sent a secure message using the electronic health record to ask permission to include their patient(s) in the study. If a physician does not explicitly respond to approve or disapprove of the identified patient(s) to participate in the study within 5 days, they are sent a reminder message; one day later, their patients will automatically be opted in to the study.

Patients approved for enrollment in the study are sent a letter informing them about the study along with a simple, one compartment per day, pillbox that allows for the storage of one week of medication. Patients are then contacted by telephone to schedule a phone consultation with the clinical pharmacist. At this time, they are also administered the Patient Activation Measure (PAM), a questionnaire to assess the knowledge, skills, and confidence to manage one's health and health care. The PAM is subsequently used to tailor the intervention for that individual patient.

Intervention

The central component of the multi-faceted intervention is an individually-tailored telephone consultation conducted by a clinical pharmacist who is part of the Harvard Vanguard care team. The

clinical pharmacists work at multiple sites; in order to reduce the chances of contamination, they are restricted to providing clinical services only at other intervention sites during the time period of this study.

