In the primary analysis, the outcomes will be compared using generalized estimating equations with an identity link function and normally distributed errors to account for the clustering of subjects within practice sites. Our primary models will also adjust for the block-randomized design. If there are differences in baseline characteristics between study groups that are believed to be confounders of the intervention–outcome association, we will repeat our analyses after adjusting for these covariates.

A similar approach will be taken for the analysis of the secondary outcomes, except using logit link functions with binary errors and log link functions with Poisson errors, as appropriate for disease control and rates of healthcare utilization, respectively.

Several additional analyses will also be conducted. First, we will assess the correlation between calculated adherence based on insurer claims, self-reported adherence, and pharmacy transaction records (for patients filling prescriptions at Harvard Vanguard pharmacies). Second, we will use Markov modeling to assess the long-term impact of the intervention on cost, quality-adjusted survival, and cost-effectiveness of the intervention.

Sample size considerations

Our study should be sufficiently powered to detect small, clinically meaningful changes in the primary outcome. We powered the study to detect a 2.5% mean change in adherence between the intervention and control groups, assuming a standard deviation of 0.25 (a conservative assumption), clustering at the practice level with a design effect of 1.10, and a 15% non-differential loss to follow-up

rate. We assumed that 95% of potentially eligible intervention patients would be approved for study inclusion by their PCPs and that 50% of these patients would agree to a pharmacist consultation. With these assumptions, we estimated that we would need a total sample size of 4000 eligible patients to provide more than 80% power to detect differences in our primary study outcome of medication adherence. In other words, if those patients receiving the intervention demonstrate a 4.6% improvement in adherence, we will still have more than 80% power to detect an improvement of 2.5% in the overall sample. We also have substantial power to detect improvements in disease control, assuming a rate of controlled disease of 30% based on our pilot data.

Summary of changes to protocol

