The independent variable of interest is exposure to the pharmacist intervention. We will measure several variables to assess the degree of balance between patients and physicians randomized to intervention versus control, to adjust for chance imbalances, and to assess whether the efficacy of the intervention is modified by particular patient characteristics. Patient demographic characteristics and major comorbid conditions, as identified based on EHR data, will be included as independent variables

HVMA currently has an existing clinical pharmacy program. These clinical pharmacists already work collaboratively with the primary care physicians in the clinics to provide patient education and advice around medication management. Primary care physicians can currently refer patients to the clinical pharmacist using an electronic referral in the electronic health record.

Final analysis plan

Sample size considerations

Our study should be sufficiently powered to detect small, clinically meaningful changes in the primary outcome. We powered the study to detect a 2.5% mean change in adherence between the intervention and control groups, assuming a standard deviation of 0.25 (a conservative assumption), clustering at the practice level with a design effect of 1.10, and a 15% non-differential loss to follow-up rate. We assumed that 95% of potentially eligible intervention patients would be approved for study inclusion by their PCPs and that 50% of these patients would agree to a pharmacist consultation. With these assumptions, we estimated that we would need a total sample size of 4000 eligible patients to provide more than 80% power to detect differences in our primary study outcome of medication adherence. In other words, if those patients receiving the intervention demonstrate a 4.6% improvement in adherence, we will still have more than 80% power to detect an improvement of 2.5% in the overall sample. We also have substantial power to detect improvements in disease control, assuming a rate of controlled disease of 30% based on our pilot data.

Outcome Measures

Primary outcome - Adherence

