The trial's primary outcome is medication adherence assessed at 12 months after randomization. Medication adherence will be assessed using prescription claims data and measured as the mean PDC over the 12 months after randomization using the "average of averages" approach used for study eligibility. Adherence will be measured only for medications that qualified a patient for inclusion in the study and follow-up will begin at the point of randomization

Secondary outcomes

The secondary outcomes for the study include disease control and rates of healthcare utilization.

Disease control will be measured as the following two different outcomes: (1) the proportion of patients achieving good disease control for all of their eligible conditions and (2) the proportion of patients achieving good disease control for at least one of their eligible conditions. Because disease control will be evaluated using biometrics that are collected during routine care rather than at study-prescribed intervals, we will use those values that are closest to each patient's 12-month end of follow-up period up to a maximum of 15 months after randomization

Rates of healthcare utilization will also be measured using administrative claims data and will include all-cause emergency room visits, physician office visits, and hospitalizations during follow-up

Statistical analyses

We will report the means and frequencies of pre-randomization variables separately for intervention and control subjects. Comparisons of these values will be performed using t-tests and chi square tests and their non-parametric analogs, as appropriate. The outcomes will be evaluated using intention-to-treat principles among all randomized patients. In the primary analysis, the outcomes will be compared using generalized estimating equations with an identity link function and normally distributed errors to account

for the clustering of subjects within practice sites. Our primary models will also adjust for the block-randomized design. If there are differences in baseline characteristics between study groups that are believed to be confounders of the intervention–outcome association, we will repeat our analyses after adjusting for these covariates.

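### The stated power of over 80% rests on an unsourced design effect of 1.10 and makes no allowance for having only 14 randomised sites; with site-level degrees of freedom it is about 70–73%

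*Combined protocol and SAP*

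**What the plan says.** The sample-size paragraph is the same in the Final protocol and the Final analysis plan. It uses a 2.5-point difference in mean PDC, an SD of 0.25 that it describes as conservative, 15% loss to follow-up, and "clustering at the practice level with a design effect of 1.10". From these, "we estimated that we would need a total sample size of 4000 eligible patients to provide more than 80% power". It gives no ICC, cluster size, source for the 1.10 or alpha, and it does not mention the number of sites.

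The Final protocol, Study design and randomization, supplies that number: "The remaining 14 Harvard Vanguard practice sites were then cluster-randomized such that all PCPs and their patients in a given practice site were assigned". Each site therefore falls wholly within one arm. On the allocation, the same section adds: "Within the resultant 4 blocks, practices were then randomized in a 1:1 ratio to intervention or control". The Background section gives 4076 patients.

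For the analysis (Final protocol, Analytic plan; Final analysis plan, Statistical analyses): "In the primary analysis, the outcomes will be compared using generalized estimating equations with an identity link function and normally distributed errors", clustered on practice site, and "Our primary models will also adjust for the block-randomized design". No small-sample variance correction, reference distribution or degrees of freedom is stated.

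**The concern.** There are two separate gaps.

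The first is the design effect. With a few hundred patients per site, a value of 1.10 requires almost no variation between sites in true mean PDC. The plan offers nothing to support that. It also says that the sites differ enough for simple cluster randomisation to risk imbalance, although blocking may absorb part of this.

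The second is the cluster count. A design effect inflates the variance for correlation within sites. It does not allow for estimating the between-site variance from only 14 sites, which calls for a t reference distribution on few degrees of freedom.

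If power is overstated, a null result may be read as stronger evidence against a 2.5-point effect than it is. If the GEE is run with an uncorrected robust variance and a normal reference, a positive result is open to challenge because the test does not hold its 5% level.

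**Working it through.** **Inputs from the documents:** difference 0.025, SD 0.25, design effect (DE) 1.10, loss 15%, N = 4000 (or 4076), 14 sites, 4 blocks, 1:1 allocation. **Assumed:** two-sided alpha of 0.05, because none is stated. It is the choice that fits: a one-sided 5% test would need only about 3,200 patients.

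**1. Reproducing the plan's figure.** Per arm, n = 2 × (1.960 + 0.842)² × 0.25² / 0.025² ≈ 1570. Then 1570 × 2 × 1.10 = 3454. Applying the loss as × 1.15 gives 3972; applying it as ÷ 0.85 gives 4064. The 4000 lies between these, so the arithmetic is sound for a normal formula.

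At N = 4000, 1700 patients per arm are analysed. SE = 0.25 × √(2 × 1.10 / 1700) = 0.00899, and 0.025 / 0.00899 = 2.780. At N = 4076 the SE is 0.00891 and the ratio 2.806.

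**2. Changing only the reference distribution.** A two-arm comparison of 14 sites has 14 − 2 = 12 df. With 4 blocks in the model it has 14 − 4 − 1 = 9 df. Noncentral t power with the same ratios:

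| | N = 4000 | N = 4076 |
|---|---|---|
| Normal (as the plan) | 79.4% | 80.1% |
| t, 12 df | 72.3% | 73.1% |
| t, 9 df | 69.7% | 70.5% |

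At N = 4000 the difference detectable with 80% power is 2.75 points (12 df) or 2.83 points (9 df). With no clustering at all (DE 1.00), 12 df gives 76% at 4000 and 77% at 4076, so the df shortfall does not depend on the ICC.

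**3. What DE 1.10 implies.** Analysed patients per site: m = 4000 × 0.85 / 14 = 242.9 (247.5 at 4076). From DE = 1 + (m − 1) × ICC, ICC = 0.10 / 241.9 = 0.00041. The between-site SD of true mean PDC is then 25 × √0.00041 ≈ 0.5 points.

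**4. Sensitivity to the ICC.** The ICCs below, taken after block adjustment, are assumptions; the documents give none. N = 4000, equal sites.

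| ICC | DE | Normal | 12 df | 9 df |
|---|---|---|---|---|
| 0.001 | 1.24 | 74% | 67% | 64% |
| 0.003 | 1.73 | 60% | 53% | 51% |
| 0.005 | 2.21 | 50% | 44% | 42% |
| 0.01 | 3.42 | 35% | 31% | 29% |

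With unlimited patients the SE cannot fall below 0.25 × √(4 × ICC / 14). So 80% power for 2.5 points is out of reach at 14 sites once the ICC exceeds about 0.0045 (normal), 0.0038 (12 df) or 0.0035 (9 df). Unequal site sizes also cost power: at ICC 0.00041 with an assumed coefficient of variation of 0.6, power on 12 df is 71%.

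**5. What happens without a correction.** Take 14 equal sites, 7 per arm, analysed through site means. The uncorrected robust variance is the usual one multiplied by 12/14, or by 9/14 with block terms (assuming blocks of 4, 4, 4 and 2 sites). A z test at 1.96 is then a t test at 1.96 × √(12/14) = 1.81 on 12 df, which rejects a true null 9.5% of the time. With block terms it is a t test at 1.96 × √(9/14) = 1.57 on 9 df, which rejects 15% of the time. Simulation at ICC 0.00041 (40,000 runs) gave 9.7% and 15%. The Kauermann–Carroll variance with a t reference rejected 5.1% and 5.2%, with power of 72% and 69%.

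**The case against.** - **The 70–73% belongs to a test the plan does not name.** Correct: the plan states no reference distribution, and its own formula does reproduce. But the alternative that keeps power near 80% is an uncorrected z test, and step 5 shows that it does not hold 5%. On these inputs the plan cannot have both. That simulation uses equal sites and assumed block sizes, so its figures are indicative.
- **The plan does allow for clustering, and the site count may already be inside the 1.10.** It does inflate for practice-level clustering. The site count may have set the cluster size, but that would still leave the df unaddressed and the ICC unsourced.
- **SD 0.25 is conservative.** This is a real offset. At N = 4000 and DE 1.10, an SD of 0.228 (12 df) or 0.221 (9 df) restores 80%. The documents give no evidence that the SD is that low.
- **Censored patients may contribute partial PDC, so the 15% loss may overstate attrition.** Possible, since the plan analyses all randomised patients. With no loss at all, N = 4076 and DE 1.10 give 79.8% (12 df) or 77.3% (9 df), still short of 80%.
- **The worst figures come from assumed ICCs.** True, and nothing in the documents makes 0.01 more likely than 0.0004. The df result does not depend on them.
- **A null result can be read from its confidence interval, and the sites are already randomised.** Also fair. It makes the variance correction the more consequential part of the remedy, because that interval is only as good as its standard error.

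**Conclusion.** The concern holds. The calculation is not an arithmetic error; it is large-sample power presented for a trial with 14 randomised units. With the plan's SD, loss and design effect and a two-sided 5% test, power for 2.5 points is 72–73% on 12 df and 70–71% on 9 df. The 9 df figure matches the block-adjusted primary model. A true 2.5-point effect would be missed about 27–30% of the time, where the plan implies under 20%.

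The design effect of 1.10 is unsupported and corresponds to an ICC of about 0.0004. Any larger ICC remaining after block adjustment lowers power further, and the documents give nothing to bound it. An SD below 0.25 would work the other way. This should be corrected before analysis.

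**What to change.** 1. State alpha and sidedness, the practice-level ICC after block adjustment with its source, and the site sizes with their variation. Derive the design effect from these.
2. Estimate the ICC from PDC data already held from screening. Eligibility requires that the average "PDC for all eligible study drugs is less than 80"%, which truncates baseline PDC, whereas 12-month PDC is not truncated. An estimate not limited to PDC below 80% is therefore preferable if those data were kept, with the caveat that it describes a wider population than the trial's. An ICC from 14 sites is imprecise, so show a range such as 0.0004 to 0.01.
3. Pre-specify a small-sample correction for the site-clustered GEE, for example the Kauermann–Carroll variance with a t reference. Fix the df in advance; 9 is the value consistent with the block-adjusted model. Use the same df in the power statement.
4. Replace the power claim with power and minimum detectable difference over the ICC range, and show sensitivity to an SD below 0.25.

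The cost is a rewritten sample-size paragraph and one added sentence on the GEE variance, with no new patients or data collection. The stated power becomes less favourable, and the interval will be wider than an uncorrected one.

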We propose a cluster randomized controlled trial (RCT) of a novel tele-pharmacist based intervention to improve adherence to medications for hypercholesterolemia, hypertension, and diabetes. We will evaluate an innovative intervention that uses of EHR data to identify approximately 2,000 adult patients cared for by approximately 170 primary care physicians who are both non-adherent and not achieving recommended clinical targets for glycemic, blood pressure, and cholesterol control in a real-world primary care setting. Following EHR-facilitated referral from the treating primary care physicians, a clinical pharmacist will direct an outreach program using multiple communication technologies including text messaging and secure email messaging to improve medication adherence.

Study design and randomization

This study is a randomized, controlled trial of patients treated at Harvard Vanguard Medical Associates. The sites involved in this study are all part of HVMA, located in Boston and surrounding cities and towns. HVMA is associated with the larger organization, Atrius Health. We will enroll all primary care physicians and their eligible patients. Eligible patients include adults 18 years and older with a diagnosis of diabetes, hypertension, or hyperlipidemia; evidence of poor disease control (see below Table); and evidence of medication non-adherence based on medication refill data. We estimate the inclusion of 170 primary care physicians and 2,000 patients.

Table. Definition of Poor Disease Control

Condition	Cardiac Risk*	Poor Control Definition
Diabetes	High	Most recent HbA1c>9
Hypertension	High	Most recent BP>140/80
	Moderate	Most recent BP>140/90
	Low	Most recent BP>150/100
Hyperlipidemia	High	Most recent LDL>100
	Moderate	Most recent LDL>130
	Low	Most recent LDL>160

* High risk defined as Framingham Risk Score (FRS≥20%) or coronary heart disease equivalent.

Moderate risk defined as 10%≤FRS<20%. Low risk defined as FRS<10%.

Intervention

Computerized Alerts to Physicians

Physicians randomized to the intervention group will receive electronic decision support tools to identify patients as non-adherent and facilitate electronic referral to the tele-pharmacist program.

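### With 14 randomized sites, a practice-level design effect of 1.10 implies an ICC of about 0.0004; the plan gives no source for it, and at SD 0.25 the claimed power has no room for a larger value

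*Combined protocol and SAP*

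**What the plan says.** The Final protocol and the Final analysis plan carry the same paragraph under Sample size considerations. The target is stated as "We powered the study to detect a 2.5% mean change in adherence between the intervention and control groups". The inputs are an SD of 0.25, which the plan calls conservative, "clustering at the practice level with a design effect of 1.10", "a 15% non-differential loss to follow-up rate", and a total of 4,000 eligible patients, said to give power above 80%. The paragraph states no ICC, no number of patients per site, no origin for 1.10, no significance level and no sensitivity range.

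The unit of randomization is in the Final protocol under Study design and randomization: "The remaining 14 Harvard Vanguard practice sites were then cluster-randomized". Allocation was 1:1 within four blocks defined by site size and by whether the site's clinical pharmacists counsel patients directly. The reason given for blocking is: "Because the practice sites differ from each other, simple cluster randomization may have resulted in imbalances in patient or provider factors". The primary model is a GEE that accounts for clustering within sites and adjusts for the blocks.

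**The concern.** A design effect means little without the cluster size. A value of 1.10 is unremarkable when clusters hold a dozen patients. When they hold more than two hundred, it says that sites hardly differ in mean adherence. The plan states the design effect alone, so a reader cannot see how strong that assumption is.

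It also sits uneasily beside the reason given for blocking. If site means had an SD of 0.5 points, the chance difference between two arms of seven sites would have an SD of about 0.5 × √(2/7) = 0.27 points. That is small for a design section concerned that site differences could bias the outcome comparison.

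At stake is how a null result is read. With power said to exceed 80% for 2.5 points, a null would be taken as evidence against an effect of that size. If the residual ICC is larger than 0.0004, that reading is not justified. With the number of sites fixed at 14, adding patients within sites does little to repair it.

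**Working it through.** **Inputs from the documents.** Difference 0.025; SD 0.25; design effect (DE) 1.10 at practice level; loss 15%; N = 4,000 (sample size sections). 14 sites, 1:1 (Study design and randomization). 4,076 patients (Final protocol, Background).

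**Assumptions.** Two-sided 5%; equal site sizes; normal approximation.

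**Step 1: reproduce the plan's N.**
- Per arm: 2 × (1.960 + 0.842)² × 0.25² / 0.025² = 1,570, so 3,140 in total.
- With DE 1.10: 3,140 × 1.10 = 3,454.
- With 15% loss: 3,454 / 0.85 = 4,064. Multiplying by 1.15 instead gives 3,973.

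Both are close to 4,000, so the stated inputs do lead to the stated N. One-sided 5% gives 3,202 and does not fit.

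**Step 2: power at the stated N.** SE = 0.25 × √(2 × DE / n per arm); power = Φ(0.025/SE − 1.960).
- 4,000 patients, 1,700 analysed per arm, DE 1.10: SE = 0.00899, power 79.4%.
- 4,076 patients, 3,464.6 analysed: power 80.1%.
- Largest DE that keeps 80% power with 3,400 analysed: 3,400 / 3,140 = 1.083.

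**Step 3: ICC implied by 1.10.** DE = 1 + (m − 1) × ICC.
- m = 4,000 × 0.85 / 14 = 242.9.
- ICC = 0.10 / 241.9 = 0.00041.
- Between-site SD = 0.25 × √0.00041 = 0.0051, or about 0.5 PDC points.
- If nobody is lost, m = 285.7 and ICC = 0.00035.
- If site sizes vary with a CV of 0.3 to 0.7 (assumed), the implied ICC falls to 0.00038 to 0.00028.

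**Step 4: sensitivity.** The documents give no ICC, so every row after the first is an assumption. There are 1,700 analysed per arm and SD is 0.25. The detectable difference at 80% power is 2.80 × SE.

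| ICC | Site SD (points) | DE | Power for 2.5 points | Difference at 80% power (points) |
|---|---|---|---|---|
| 0.00041 (implied) | 0.5 | 1.10 | 79.4% | 2.5 |
| 0.001 | 0.8 | 1.24 | 74% | 2.7 |
| 0.002 | 1.1 | 1.48 | 67% | 2.9 |
| 0.005 | 1.8 | 2.21 | 50% | 3.6 |
| 0.01 | 2.5 | 3.42 | 35% | 4.4 |
| 0.02 | 3.5 | 5.84 | 23% | 5.8 |

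If all 4,000 are analysed, power is 80% at ICC 0.001 (79.7%), 53% at 0.005 and 36% at 0.01, so the loss assumption matters little once the ICC is not tiny.

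**Step 5: effect of a smaller SD.** At SD 0.22 (illustrative), the total before inflation is 3,140 × (0.22/0.25)² = 2,432. Then 80% power tolerates DE = 3,400 / 2,432 = 1.40, or ICC = 0.40 / 241.9 = about 0.0016.

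**The case against.** The strongest defence is that 1.10 may be meant as a residual value. The two site features the design section names, size and pharmacist counseling, are the blocking factors, and the primary model adjusts for the blocks. Eligibility also requires average PDC below 80% at every site, which may narrow site differences. The SD is described as conservative, and Step 5 shows that a modest reduction buys some room. All of this stands as possibility. None of it is quantified, and the plan does not say that 1.10 is residual. Two binary factors would have to leave a site SD of about 0.5 points.

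It is also fair that the shortfall on the plan's own inputs is under one percentage point, that 4,076 patients close it, and that power is still 67% to 74% at ICC 0.001 to 0.002. The design effect is a planning figure. It does not enter the GEE estimate.

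Two stronger readings are tempting. A reader might infer that the design section contradicts 1.10. It does not: it gives a conditional, qualitative reason for blocking and no variance for PDC. There is tension between the two, not contradiction.

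A reader might also infer that 1.10 was carried over from the superseded physician-level design, with "approximately 2,000 adult patients cared for by approximately 170 primary care physicians", or about 12 per cluster (2,000/170 = 11.8). The documents do not support this. The Summary of changes to the analysis plan says the original plan held no detailed sample size calculation, the current text ties 1.10 to the practice level, and the enrolment target was revised in February 2016, after the March 2015 submission that moved randomization to sites. Any design effect can be turned into some ICC at any cluster size, so a plausible fit does not show where it came from.

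**Conclusion.** The point holds as one about an unsupported input, not an arithmetic slip: the stated N reproduces. A practice-level design effect of 1.10 with about 243 analysed patients per site means an ICC of about 0.0004, residual if blocking is credited. At SD 0.25 and two-sided 5%, 80% power with 3,400 analysed allows a design effect of at most 1.083. The claim of power above 80% is therefore not strictly met by 4,000 patients, is only just met by 4,076, and fails at any ICC of 0.001 or more.

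How far it fails is unknown, because the documents give no ICC. The range of 74% down to 23% is conditional on assumed ICCs of 0.001 to 0.02, equal site sizes, the normal approximation, and no credit for blocking or a smaller SD. It would go too far to say that the trial is shown to be underpowered. What can be said is that the claimed power has no documented basis at the site level. This should be fixed; it does not call the design or the primary model into question.

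**What to change.** In both sample size sections:

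1. Replace the bare 1.10 with DE = 1 + (m − 1) × ICC, using m of about 243 and the actual site sizes, and state alpha and sidedness.
2. Estimate the ICC, with and without block adjustment, from 12-month PDC pooled without arm labels. Use baseline PDC only as a first estimate, because eligibility truncates it below 80% and it may understate the outcome ICC. A pooled ICC also absorbs any true arm difference: 2.5 points would add about 0.0125² / 0.25² = 0.0025. Say so, and report the within-arm ICC with the primary results.
3. Restate power for 2.5 points and the detectable difference at 80% power over ICC 0.001 to 0.02. Fourteen sites estimate an ICC imprecisely, so keep the range even once an estimate exists.
4. Remove the claim of power above 80% unless the estimated ICC supports it.
5. State that a null result will be read against the confidence interval and the restated detectable difference.

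The cost is one paragraph in each document and an ICC from data the trial collects anyway. No patients are added, and the endpoint and model do not change. The downside is that the stated power will probably be less favourable.
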